6.1.2 Descriptive analyses

TSH levels will be summarized over time together with their changes from baseline. The frequency of TSH responders will be summarized for each timepoint. Same statistical analysis will be performed for the frequency of patients whose total T3 and free T4 levels normalize. Results will also be presented for free T3 and total T4.

6.1.3 Statistical model, assumptions and hypotheses

One of the main efficacy criteria for this study is to show that the proportion of patients with normalization of TSH (above 0.35 mU/L) after 12 weeks of treatment with CFZ533 is statistically greater than 5%, according to a 1-sided exact test for proportions with a 10% type I error. This will be achieved if we observe at least 3/12 responders since in that case the lower bound of an 80% confidence interval for the proportion of responders will be about 10%. The other efficacy criteria are that there is a significant reduction in average total T3 and free T4 after 12 weeks of treatment, according to a 1-sided paired t-test with 10% type I error for each of these two endpoints. Results will also be presented for free T3 and total T4 and at week 20.

6.1.3.1 Handling of missing values/censoring/discontinuations

Patients who discontinue after the 4 week efficacy assessment for any reason will be considered non-responders in the primary analysis (unless their last recorded TSH value was after 8 weeks of treatment and was above the lower limit of the normal range, 0.35 mU/L). Patients who discontinue before 4 weeks of treatment for any reason will be replaced and not counted for the calculation of responders. For total T3 and free T4, the last recorded value will be used for the change from baseline (Day 1, predose), provided it was obtained after at least 8 weeks of treatment.

6.1.3.2 Supportive analyses

In case more than 2 discontinuations occur in this study, additional methods may be used to assess sensitivity of the results to different imputation techniques to deal with the missing data.

Total and free T3 and T4 will be analyzed using a repeated measures model with baseline as a covariate and visit as the repeated effect. The difference from Day 1 at each timepoint will be presented along with the 80% CI and the 2 sided p-value.

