11.6 Sample size calculation

The proposed sample size for this study is 12 patients (to complete the study). Assuming CFZ533 is associated with 38% normalization of the TSH levels after 12 weeks of treatment (which is consistent with the response rate seen with Rituximab in 26 weeks in one small, open-label study ([Heemstra et al 2008](#)), there is around 89% power to detect a proportion of TSH responders significantly higher than 5% (this would be achieved with at least 3/12 responders), with a type I error of 10%. Additionally, this sample size provides 98% power to detect normalization of the total T3 (and free T4, respectively) below the upper limit of the normal range (2.79 nmol/L and 22.7 pmol/L, respectively). The assumed baseline levels are 7.2 nmol/L for total T3 and 58.55 pmol/L for free T4, which are the average values reported in GD patients in [Andrade et al \(2001\)](#). The assumed standard deviation for the change from baseline are 4.24 nmol/L and 34.58 pmol/L respectively.

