1.4 Study design and treatment

This is a non-confirmatory, open-label, one treatment arm study in patients with newly diagnosed GD.

A total of approximately 15 patients will be enrolled and treated with CFZ533 to ensure approximately 12 completers. For each patient, the study will consist of a screening epoch of up to 28 days, a baseline evaluation, a 12-week treatment epoch, 24-week follow up epoch after the last dosing of CFZ533 on Study Day 85, and a study completion evaluation on Study Day 253. Patients who discontinue the drug before having completed 4 weeks of treatment and 4 week efficacy and safety evaluations will be replaced with a newly enrolled patient. The study design is presented in Figure 1-1.

Figure 1-1 Study design

2 First interpretable results (FIR)

First interpretable results (FIR) will be provided for this trial.

The study FIR template (mock slides) can be found in CREDI in the study RAP folder.

The template shows the analysis / results to be presented in the FIR. Study outputs required to be created at the time of the FIR will be highlighted in TFL shells document and marked as "Key" in the Programming Deliverables Tracker (PDT) output list.

3 Interim analyses

Corporate Confidential Information

4 Statistical methods: Analysis sets

For all analysis sets, patients will be analyzed according to the study treatment received.

All patients that received study drug and with no protocol deviations with relevant impact on safety will be included in the safety analysis set.

The PK analysis set will include all patients with at least one available valid (i.e. not flagged for exclusion) PK concentration measurement, who received any study drug and experienced no protocol deviations with relevant impact on PK data.

The PD analysis set will include all patients with any available PD data, who received any study drug and experienced no protocol deviations with relevant impact on PD data, who have completed at least 4 weeks of treatment with CFZ533.

The analysis sets and protocol deviation codes are related as follows:

Table 4-1 Protocol deviation codes and analysis sets

Category Deviation code	Text description of deviation	Data exclusion
Subjects are excluded from all (safety) analysis in case of these PDs:		
I01	Deviation from inclusion criteria 1 (ICF not obtained)	Yes
	No study drug taken	Yes
Subjects are excluded from PK analysis in case of these PDs:		
I01	Deviation from inclusion criteria 1 (ICF not obtained)	Yes

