6.1.1 Variables

The effects of CFZ533 on thyroid function will be primarily assessed by the proportion of

patients whose TSH levels normalize (above 0.35 mU/L) after 12 weeks of treatment (TSH responders). They will also be assessed by the difference in mean total T3 and free T4 between baseline (Day 1, predose) and after 12 weeks of treatment, and the proportion of patients whose total T3 or free T4 levels normalize (below ULN) after 12 weeks of treatment.

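### In this one-arm study, the baseline-adjusted supportive model for T3 and T4 gives an 80% CI that is generally too narrow for the mean change from Day 1

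*SAP*

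**What the plan says.** SAP 1.4 describes a "non-confirmatory, open-label, one treatment arm study". For total T3 and free T4, SAP 6.1.1 sets the target as the "difference in mean total T3 and free T4 between baseline (Day 1, predose) and after 12 weeks of treatment". SAP 6.1.3 tests this "according to a 1-sided paired t-test with 10% type I error for each of these two endpoints".

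SAP 6.1.3.2 adds a supportive analysis of total and free T3 and T4 using "a repeated measures model with baseline as a covariate and visit as the repeated effect". Its output is defined as follows: "The difference from Day 1 at each timepoint will be presented along with the 80% CI and the 2 sided p-value".

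The SAP does not give the baseline value at which the estimate is taken, the covariance structure, or any baseline-by-visit term. It does not say whether Day 1 is also a response level, or whether the SE allows for baseline being sampled. Nothing restricts the inference to patients with the observed mean baseline. SAP section 4 excludes post-rescue data from the inferential analyses and relies on the longitudinal models being unbiased under missing at random (MAR).

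**The concern.** Adjusting for baseline is routine in a two-arm trial, where the sampling error of the baseline mean largely cancels in the treatment difference. Here there is no second arm. The mean change is itself the estimand, and chance variation in the mean baseline carries through to it. A model that treats the observed baselines as fixed drops that part of the error.

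The model covers four hormones at every visit. It is also the analysis that readers will turn to if rescue treatment is common, because it carries the MAR handling. The study is meant to inform whether development continues, so intervals from about 12 patients that look tighter than they are would overstate how well the change is known.

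**Working it through.** **Inputs from the documents.** Protocol 11.6 states: "The proposed sample size for this study is 12 patients (to complete the study"). It also states: "The assumed baseline levels are 7.2 nmol/L for total T3 and 58.55 pmol/L for free T4". The targets are 2.79 nmol/L and 22.7 pmol/L, and the SDs of change are 4.24 nmol/L and 34.58 pmol/L. The main test is a one-sided 10% paired t-test.

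**Not in the documents.** The Day 1 SD, the follow-up SD and their correlation are not given. They are assumed below and shown over a range.

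**1. Reproduce the plan's own figure.** For total T3 the SE is 4.24/sqrt(12) = 1.224, and the noncentrality is (7.2 - 2.79)/1.224 = 3.60. For free T4 the SE is 34.58/sqrt(12) = 9.98, and the noncentrality is (58.55 - 22.7)/9.98 = 3.59. With 11 df and one-sided 10%, power is 98.5% for each. The stated 98% reproduces.

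**2. The paired interval.** The t quantile for a two-sided 80% CI with 11 df is 1.363. The half-width is 1.363 x 1.224 = 1.67 nmol/L for total T3 and 1.363 x 9.98 = 13.6 pmol/L for free T4.

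**3. The model interval at one visit, complete data.** Regress change on baseline and evaluate at the sample mean baseline. The estimate equals the raw mean change. The model SE is SD(change) x sqrt(1 - r^2)/sqrt(n), with n - 2 = 10 df (t quantile 1.372). The omitted variance is slope^2 x baseline variance/n.

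Under normality the mean change is independent of the residual variance. So (estimate - true mean change)/model SE is a t variable on 10 df divided by sqrt(1 - r^2). Hence:

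- real coverage = P(|T10| < 1.372 x sqrt(1 - r^2))
- real one-sided error at nominal 10% = P(T10 > 1.372 x sqrt(1 - r^2))

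**4. Link r to the assumed inputs.** Let k be follow-up SD/Day 1 SD and c the Day 1 to follow-up correlation. Then r = (kc - 1)/sqrt(1 + k^2 - 2kc), which gives 1 - r^2 = k^2(1 - c^2)/(1 + k^2 - 2kc).

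| k | c | r | sqrt(1 - r^2) | coverage of 80% CI | one-sided error at 10% |
|---|---|---|---|---|---|
| 1 | 0 | -0.71 | 0.71 | 65% | 18% |
| 1 | 0.5 | -0.50 | 0.87 | 74% | 13% |
| 1 | 0.8 | -0.32 | 0.95 | 78% | 11% |
| 0.5 | 0 | -0.89 | 0.45 | 45% | 28% |
| 0.5 | 0.5 | -0.87 | 0.50 | 49% | 25% |
| 0.5 | 0.9 | -0.93 | 0.37 | 38% | 31% |
| 1.5 | 0.7 | 0.05 | 1.00 | 80% | 10% |

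Simulation at n = 12 (100,000 runs per scenario) agrees, and the paired t interval stayed at 80% throughout. For k below 1, sqrt(1 - r^2) cannot exceed k (its maximum is at c = k). So at k = 0.5 or less, coverage is at most 49%.

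At the planned SD of change for total T3, the model half-width is 1.372 x 1.224 x 0.707 = 1.19 nmol/L for k = 1, c = 0, and 1.372 x 1.224 x 0.866 = 1.45 nmol/L for k = 1, c = 0.5. The paired half-width is 1.67.

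**5. Conditional reading.** Conditional on the observed mean baseline, the same model intervals cover 80%.

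**6. Several visits.** A five-visit model with compound symmetry (400 runs per scenario, simulation error about 2 points, some convergence warnings) gave:

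- change as the response: coverage 66% at correlation 0 and 78% at 0.5
- Day 1 also kept as a response level: 70% and 82%

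**The case against.** The strongest reply is that the text does not fix the implementation. A difference from Day 1 can be read as a contrast with a Day 1 response level. The shortfall then depends on the covariance structure, and in one scenario above it disappeared within simulation error. The TFL shells mentioned in SAP section 2 may settle these details. This stands: the result holds under the usual reading, and the gap in specification is part of the point.

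Other limits also stand. The study is non-confirmatory, no visible decision rule uses this model, and the narrowing is largest where the planned effect already gives the paired test 98.5% power.

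A reader might infer four stronger things that the documents do not support.

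- **That the model p-value will be smaller than the main test's.** The model reports a two-sided p-value and the main test is one-sided. With no effect, equal SDs and correlation 0.5, the model's two-sided p exceeds the paired one-sided p in 92% of samples showing a decrease. The p-value is too small only like for like. In that scenario a decrease with two-sided p below 0.10 occurs P(T10 > 1.812 x 0.866) = 7.4% of the time, against a nominal 5%.
- **That both analyses will give the same Day 85 estimate.** This needs complete data. SAP 6.1.3.1 carries forward a last value obtained after at least 8 weeks, while the model relies on MAR, so dropout or rescue can separate them.
- **That coverage below 50% is a property of the plan.** It requires a follow-up SD of about half the Day 1 SD or less. That is plausible if treatment normalises hormones, but the documents do not give it.
- **That the efficacy criteria are compromised.** They are not; only the supportive model is affected.

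**Conclusion.** The concern holds for the supportive model. With the estimate taken at the sample mean baseline and the default SE, the 80% CI describes patients with the observed mean baseline. It is generally too narrow for the population mean change that SAP 6.1.1 names, by a factor of about sqrt(1 - r^2) in the SE. Baseline adjustment does not bias the complete-data point estimate.

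The size cannot be fixed from the documents. With 12 patients and equal SDs it ranges from slight (78% coverage at correlation 0.8) to material (65% at correlation 0). It is larger if follow-up values are much less variable than Day 1 values, and nil if change is uncorrelated with baseline. The figures assume normal data, complete follow-up and a single-visit fit. It should be corrected in the SAP, but it does not threaten the study's main efficacy tests.

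**What to change.** In SAP 6.1.3.2, drop the baseline covariate. Fit Day 1 and all post-dose values as responses, with visit as a fixed factor, and report visit-minus-Day 1 contrasts with the 80% CI. With complete data and an unstructured covariance this reproduces the paired estimate and SE.

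State the covariance. Days 1, 15, 29, 57 and 85 need 5 x 6/2 = 15 parameters. All ten visits to Day 253 would need 10 x 11/2 = 55, which about 12 patients will not support. So use an unstructured covariance where it can be fitted, for example Days 1 to 85. For later visits or non-convergence, choose one of:

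- a named simpler structure with an SE that still reflects Day 1 sampling variation, such as a patient-level bootstrap; a simpler structure with its default SE would not generally match the paired SE
- a separate joint fit of each visit with Day 1, noting that MAR then conditions on Day 1 alone

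Alternatively, keep the covariate and add the baseline-mean variance (slope^2 x baseline variance/n) to the squared SE, or bootstrap patients. Both main routes keep the MAR handling of post-rescue data in SAP section 4. The two-sided p-value can stay, with a note that it is not directly comparable with the one-sided paired p-value.

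The cost is a few sentences of SAP text, a small program change and generally wider reported intervals.

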6.1.3.3 Graphical presentation of results

Mean (SD) TSH levels and Mean (SD) change from baseline in TSH levels will be plotted over time. Overlaying TSH level profiles will also be presented. Similar figures will be presented for total and free T3 and T4. Overlaying profiles will have separate pages for all

subjects, subjects that have received rescue medication and subjects that received no rescue with the time of the start of the rescue medication indicated on the plot.

Bar charts of the number of TSH responders will be plotted over time. Similar bar charts will be plotted for the frequency of patients whose total and free T3 and T4 levels normalize.

6.2 Secondary and exploratory objectives

6.2.1 Variables

Corporate Confidential Information

6.2.2 Descriptive analyses

Corporate Confidential Information

6.2.2.1 Graphical presentation of results

Corporate Confidential Information

7 Statistical methods for safety and tolerability data

7.1.1 Variables

Adverse events, vital signs (blood pressure, pulse rate, body temperature), ECG intervals, laboratory measurements, as well as patient demographics, baseline characteristics, and treatment information.

7.1.2 Descriptive analyses

Patient demographics and other baseline characteristics

All data for background and demographic variables including background medication (type of medication and mean dose per day, with the average prednisone equivalent dose in mg presented for steroids) will be listed by treatment group and patient. Summary statistics will be provided by treatment group.

Relevant medical history, current medical conditions, results of laboratory screens, drug tests and any other relevant information will be listed by treatment group and patient.

Treatment

Data for study drug administration (rescue medication) and concomitant therapies will be listed by treatment group and patient.

Vital signs

All vital signs data will be listed by treatment, patient, and visit/time and if ranges are available abnormalities (and relevant orthostatic changes) will be flagged. Summary statistics will be provided by treatment and visit/time.

ECG evaluations

All ECG data will be listed by treatment, patient and visit/time, abnormalities will be flagged. Summary statistics will be provided by treatment and visit/time.

Clinical laboratory evaluations

All laboratory data will be listed by treatment, patient, and visit/time and if normal ranges are available abnormalities will be flagged. A separate listing is provided presenting all parameters in a patient with any abnormal values. Summary statistics will be provided by treatment and visit/time.

Adverse events

All information obtained on adverse events will be displayed by treatment and patient.

The number and percentage of patients with adverse events will be tabulated by body system and preferred term with a breakdown by treatment and repeated for adverse events that were suspected to be related to the study medication. A separate table will also be produced for adverse events of infection. A patient with multiple adverse events within a body system is only counted once towards the total of this body system and treatment.

Corporate Confidential Information

7.1.3 Graphical presentation

Boxplots to visualize trends in longitudinal safety data (vitals, ECG, lab parameter) will be created.

8 Statistical methods for Biomarker data

Corporate Confidential Information
